5.3 Tertiary endpoints

Tertiary endpoints will be measured continuously during ventilation period **from day 8 up to day 28** after enrollment.

Efficacy

Efficacy of the investigational device by assessing the ability to keep ventilation and oxygenation variables in optimal target ranges.

This endpoint will be determined by the percentage of time spent with six (6) variables in the optimal range:

- 1) Tidal volume (VT)
- 2) Maximum pressure (Pmax)
- 3) Oxygen saturation measured by pulse oximetry (SpO₂)
- 4) End-tidal partial pressure of carbon dioxide (PetCO₂)
- 5) Respiratory rate (RR) for spontaneous breathing subjects
- 6) Pmax-PEEP for passive ARDS subjects

The optimal and sub-optimal ranges are defined by pertinent guidelines for different clinical conditions including normal lungs, brain injury, ARDS, and chronic hypercapnia.

Tertiary endpoints will be measured continuously during ventilation period **from day 8 up to day 28** after enrollment.

Safety:

The tertiary safety endpoint will be determined by percentage of time spent with at least one variable in the sub-optimal range **from day 8 up to day 28 after enrollment**.

6 STUDY DESIGN

6.1 General

EASiVENT is a Pivotal, two-arm, controlled, single-blind, multicenter, randomized trial of INTELLiVENT-ASV versus non automated Ventilation in adult ICU subjects.

6.2 Methods of minimizing bias

6.2.1 Randomization

The subjects will be randomized to either INTELLiVENT-ASV or Non automated Ventilation using in a 1:1 ratio by a computerized central randomization system.

The two study arms will be stratified by subject condition at inclusion (normal lungs, ARDS, chronic hypercapnia, or brain injury) and by site to ensure balanced assignment for interventions at each site. The randomization scheme will be generated and maintained by the randomization module part of the electronic case report form (eCRF).

6.2.2 Blinding

Study subjects will be blinded to the random intervention assignment. Therefore, this study is considered single blind since study staff will know each subject's intervention assignment.

6.3 Justification for the design of the clinical investigation

The reference treatment used for comparison is a combination of controlled modes for passive subjects (volume control or pressure control) and assisted/spontaneous modes for active subjects (synchronized intermittent mechanical ventilation or pressure support).

Sample size has been adjusted with an adaptive design to be able to fulfill the targeted endpoints (see section 10.2)

7 STUDY POPULATION

7.1 Selection of the Study Population

Eligible patients are adult ICU subjects, 21 years and older, requiring invasive mechanical ventilation and fulfilling the inclusion and exclusion criteria.

ICU patients will be selected from sites in Europe and in US. Recruitment will be competitive.

7.2 Inclusion Criteria

Subjects must fulfill all of the following inclusion criteria to be eligible for enrollment into this study:

1. Age \geq 21 years old
2. Weight > 40 kilograms
3. Under invasive ventilation for less than 24 hours
4. Expected to be mechanically ventilated for at least 24 hours after enrollment
5. Agrees to not participate in other interventional research studies involving mechanical ventilation for the duration of study participation, unless approved by the DSMB
6. Signature of the informed consent by the subject or his/her next-of-kin according to country or state regulation

7.3 Exclusion Criteria

Subjects who meet any of the following criteria are not eligible for enrollment into this study:

1. Fulfilling weaning criteria according to the weaning procedure of the ICU
2. Need for “rescue therapy” (ECMO, ECCO2R, HFO))
3. Brain death status
4. Respiratory drive disorder (Cheyne-Stokes breathing)
5. Arterial hypoxia due to a non-pulmonary condition (right-to-left shunting due to congenital disease, hepato-pulmonary syndrome,)
6. Broncho-pleural fistula
7. Chronic or acute dyshemoglobinemia: acute CO poisoning, meth-hemoglobin, sickle cell disease.
8. Chronic respiratory failure requiring long term invasive ventilation;
9. Moribund subject: death expected within 24 hours
10. Positive pregnancy test at screening for childbearing age women
11. Decision to withhold or withdraw life support. This does not exclude those patients committed to full support except cardiopulmonary resuscitation.
12. Subject under guardianship
13. Subject deprived of liberties
14. Subject included in another interventional research study involving mechanical ventilation under consent.

15. Any other condition, that in the opinion of the IoR/designee, would preclude informed consent (by the spouse/next of kin), make study participation unsafe, complicate interpretation of study outcome data, or otherwise interfere with achieving the study objectives.
16. Low quality index on the SpO₂ measurement using finger and ear sensor for > 3 hours
17. Subjects already enrolled in the present study in a previous episode of acute respiratory failure
18. High PaCO₂ – ETCO₂ gap (> 2.6 kPa or 19.5 mmHg) for > 3 hours
19. Patient tracheostomized at the time of inclusion
20. Patient ventilated with helium

7.4 Vulnerable Population

Pregnant Women

Any female with childbearing potential that tests positive for pregnancy at screening is not eligible to participate in this study.

Subject under guardianship/ Subject deprived of liberties

Any subject who is under guardianship or deprived of liberties is not eligible to participate in this study.

Children

This study will not enroll persons under the age of 21 years.

7.5 Co-enrollment Guidelines

As indicated in Sections 7.2 and 7.3 above, subjects are not permitted to take part in other research studies involving mechanical ventilation for the duration of study participation while taking part in *EASiVENT*, unless approved by the DSMB. Should any participant (or friend, family member, etc.) report concurrent participant in another research study after enrollment into *EASiVENT* not previously approved by the DSMB, the IoR/designee must consult the DSMB regarding ongoing participation and potential safety considerations associated with co-enrollment.

7.6 Study Withdrawal

Participants (or spouse/next of kin or legally authorized representative) may voluntarily withdraw from this study for any reason at any time, regardless of the participant retention strategies utilized. Additionally, the IoR may also withdraw participants from the study in order to protect their safety and/or if they are unwilling or unable to comply with required study procedures after consultation with primary investigator and Hamilton Medical. Participants may be withdrawn from the study if the study sponsor, government or regulatory authorities (including Office for Human Research Protections [OHRP] and the FDA) or site IRBs/ECs terminate the study prior to its planned end. Every reasonable effort will be made to complete a final evaluation of participants who withdrawal/terminate early from the study, and study

staff will record the reason(s) for all withdrawals in the participants' study records. In addition, subject withdrawal will be documented in the eCRF on the End of Study forms.

If subjects are transferred after seven (7) days of start of ventilation, primary endpoints will be assessed and study ventilation protocol ended. However, the ventilation duration and mortality will be captured on Day 28 after enrollment via a phone call as described in VFD section.

Dropout could occur when patients are ventilated for less than 24 hours after inclusion because of unexpected death, transfer to another ICU, or withdrawal of informed consent. We expect a maximum of 5% of these cases.

Note a maximum of 5% of subjects are anticipated for which not 80% of mechanical ventilation time, within the allocated randomized ventilation mode, could be recorded due to documented technical reason.

Please refer to: Section 10.5 “Missing Data”

7.6.1 Lost-to-follow-up

A subject is to be considered lost to follow-up once the investigator and/or research staff has made three documented attempts to contact the subject in case of Day 28 data collection and the subject is not reachable. The third attempt should be made by certified mail to the subject.

In case the required data of Day 28 is available in the national/site database there is no need to send out a certified mail to the subject.

7.7 Medical care after study exit

After the subjects exit the study (Day 28 data collection completed), the subject will be followed as per routine standard of care. No long-term follow-up is planned per the protocol.

7.8 Informed Consent Process

Written informed consent will be obtained from each study participant, spouse/next of kin or a legally authorized representative. As the protocol is dealing with ICU subjects, it is anticipated that most of subjects are in a life-threatening situation and it is not feasible to obtain their informed consent as a result of their medical condition. In that case, a legally authorized representative or a family member of the subject will be asked to provide consent and that he or she may discontinue the subject's participation at any time without penalty or loss of benefits to which the subject is otherwise entitled. If a legally authorized representative or family member is told about the clinical investigation and the subject's condition improves, the subject is also to be informed as soon as feasible.

Each study site will have their site specific study informed consent form(s) for local use that describes the purpose of the study, randomization and the importance of participation in both study interventions to the success of the study, the procedures to be followed, the risks and benefits of participation, the distinct between research and clinical care, and the right to withdraw from the study at any time, in accordance with all applicable regulations. If applicable, the study site is also responsible for translating the template form into the local language, and verifying the accuracy of the translation by performing an independent back-translation.

All USA sites will cover the elements required per Office for Human Research Protections (OHRP) CFR §46.116 - Informed Consent Checklist - Basic and Additional Elements in their local consent forms.

Each participant (or spouse/next of kin or a legally authorized representative) will document his/her provision of informed consent by signing his/her informed consent form.

Each signed and dated consent must be maintained by the clinical investigator and a copy of the informed consent must be provided to the subject.

8 STUDY PROCEDURES

8.1 Screening and Point of Enrollment process

8.1.1 Screening

Patient's eligibility will be determined by the investigator or designee based upon the followings:

1. **The availability of Hamilton's ventilators** designated for the study.
 - a. If subject's participation will be waived due to lack of device availability it will be documented on the study Pre-Screened subjects log.
 - b. If the number of eligible patient is greater than the number of the available ventilators that are designated for the study, the chronological order to ICU admission (date & time) must be respected.
2. **Site personnel workload assessment:**
If subject's participation will be waived due to resource limitation of the study team, the chronological order to ICU admission (date & time) must be respected and the reason will be documented on the study Pre-Screened subjects log.
3. **Pregnancy test** (for female subjects of childbearing potential). Test must be completed per institutional standard of care at the time of screening. Results must be negative.
4. Investigators or designee will assess if the potential patient is expected to be on invasive mechanical ventilation for more than 24 hours based upon review of their medical history and disease progress for inclusion in the trial.

If the patient appears to meet the eligibility criteria, and is expected to be ventilated for more than 24 hours:

- a. Then the investigator will discuss the study with the patient or next-of-kind or a legally authorized representative and provide information relating to the potential risks and benefits, and required follow-up procedures per the informed consent process, and
- b. The investigator will check that the patient did not express his/her right to object to participate in the study in any identifiable manner, including obtaining clear oral information from any available relative(s) on the patient's will.

After the patient or next-of-kind or a legally authorized representative has voluntarily signed and dated the Informed Consent Form (ICF), the patient will be considered as a study candidate.

If the patient and or the next-of-kind or a legally authorized representative does not sign the ICF or the patient expressed his/her right to object to participate in the study in any identifiable manner, then no further study specific screening procedures can occur.

The consenting process has to be documented in the subject source data.

8.1.2 Point of Enrollment and Randomization:

Subjects or next-of-kind or a legally authorized representative who sign and date the ICF and meet all of the study eligibility criteria will be eligible for inclusion into the EASiVENT Study.

Two different scenarios might occur:

1. The patient is already under invasive ventilation (intubated) for less than 24 hours, the next-of-kind or a legally authorized representative will sign and date the ICF.
2. The patient is able to sign and date the ICF before intubation.

The subject will only be considered enrolled when the **ICF signed and dated** and the subject will be **randomly assigned (1:1)** to automate ventilation with INTELLiVENT-ASV or to the non-automated ventilation.

Randomization will be stratified according to the clinical condition at inclusion (normal lungs, ARDS, chronic hypercapnia, brain injury). According to randomization allocation, the subject's attending physician will adjust the ventilator settings and recording will start.

Recording of ventilation data will start as randomization is completed and allocated randomization mode is selected.

Enrolled subjects will be documented on the Screening and Enrollment Log.

The investigator will maintain a log of all subjects screened and enrolled in the clinical study, assigning an identification code linked to their names, alternative subject identification or contact information. Patients who do not qualify for enrollment will be documented as ineligible on the Screening and Enrollment log.

Adverse Event collection will be started after point of enrollment.

8.2 Baseline Assessment (Day 0)

Collection of baseline information will take place only after the subject or next-of-kind or a legally authorized representative has given voluntary, documented informed consent and will include the following:

- Intubation status
- Demographic data : gender, age, height (measured at entry time), actual weight;
- Vital signs: blood pressure, pulse rate and temperature
- Subject comorbidity & medical history (including pulmonary and cardiovascular medical history) and acute pulmonary condition;
- Ventilator parameters manual assessment
- 24h Recording of ventilation parameters (Memory Box)

- Concomitant rescue therapies (proning, Nitric oxide, ...)
- Acute Kidney Injury (AKI) status and need for RRT (yes/no)
- Critical illness encephalopathy status (yes/no)
- Blood gas analysis
- Critical illness polyneuro-myopathy status (yes/no)
- Adverse Event collection

All concomitant medications including sedation, analgesic, myorelaxants, concomitant vasopressors, inotropics use and the drugs used to treat chronic diseases.

Ventilation start date/time as well as ventilation parameters will be recorded in the eCRF.

In addition, main ventilation variables used for analysis will be recorded breath by breath:

- Tidal volume (VT);
- Respiratory rate (RR);
- Maximum pressure (Pmax);
- Oxygen saturation measured by pulse oximetry (SpO₂);
- End-tidal partial pressure of carbon dioxide (PetCO₂).

Plateau pressure and total PEEP will be measured by inspiratory and expiratory occlusions respectively at regular intervals and recorded in the electronic Case Report Form (eCRF) twice a day during the passive ventilation period.

8.3 Intervention Period (Day 1-Day 27):

8.3.1 General management in both groups

From inclusion up to day of extubation (and not reintubated within 48h after extubation), ventilation settings will be adjusted by the attending physician or respiratory therapist. Subject condition, sedation, analgesic and vasopressor use, and one blood gas analysis will be collected twice a day if blood gas analysis is done routinely by the ICU department, otherwise ventilation parameters will only be collected.

Subjects will be monitored by the attending physicians and all ventilation variables will be continuously recorded from inclusion to extubation or death. Except for ventilation, all other procedures and care (sedation, hemodynamics, glycemic control, etc.) will be conducted according to the protocols of the site by the subject's attending physicians.

Data listed below will be captured in the eCRF:

- Intubation/reintubation status
- INTELLIVENT-ASV randomization violation status
- Vitals signs: Blood pressure, pulse rate and temperature;
- Acute pulmonary condition;
- 24h Recording of ventilation parameters (Memory Box)

- Ventilation settings
- All concomitant medications including sedation;
- SOFA will be repeated at day 3 and 7, in order to follow the evolution of organ failure.
- Memory Box recording
- Blood gas analysis
- Severity scores based on the most abnormal values in oxygenation and laboratory results in the last 24h period (day 0):
 - Simplified Acute Physiology Score (SAPS II)
 - Acute Physiology and Chronic Health Evaluation (APACHE II)
 - SOFA score
- Concomitant sedation, analgesia and myorelaxants use
- Concomitant vasopressors and inotropics use
- Number of recruitment movers within the last observation period
- Concomitant rescue therapies (proning, Nitric oxyde, ...)
- Weaning information associated interventions (Patient Passive/Active but still on MV, NIV, CPAP, High Flow.)
- Advers Event collection

Recorded data has to be 24 hours at minimum and 80% of the invasive ventilation duration within the allocated randomized ventilation mode have to be recorded in the in Memory Box.

If the subject's medical condition requires medical intervention (bronchoscopy, trancescopy, radiology or OR interventions...etc) and the subject is allocated to the INTELLiVENT-ASV arm, the allocated randomized ventilation mode may be switched off for the required time period. This needs to be documented in the subject's medical chart.

Dropout could occur when patients are ventilated for less than 24 hours after inclusion because of unexpected death, transfer to another ICU, or withdrawal of informed consent. We expect a maximum of 5% of these cases. Note a maximum of 5% of subjects are anticipated for which not 80% of mechanical ventilation time could be recorded within the allocated randomized ventilation mode due to documented technical reason. The recorded data will be used (with 'percent spent' calculated per the recorded time) for the primary analysis of the co-primary endpoints. As a sensitivity analysis, these values will be treated as missing data.

If the ventilation mode is modified by the site personnel by oversight or lack of training (deviating from the allocated randomization arm) and the subject's medical condition did not require it, the ventilation mode should be set back to allocated randomization arm. A protocol deviation and the event will be recorded in the eCRF accordingly.

If the site's principal investigator determines that the study is no longer in the subject's best interest (including the randomized ventilation mode) the subject's ventilation and study data collection ends. The site needs to complete an AE and the End of Study eCRF.

A. Gas exchanges targets:

SpO₂ will be kept in the ranges:

- 94 - 98% for normal lung, mild and moderate ARDS, and brain injured subjects
- 90-96% for moderate ARDS
- 88 - 95% for severe ARDS
- 90 - 94% for COPD without chronic hypoxemia or hypercapnia
- 88 - 92% for chronic hypercapnic subjects or subjects on long term oxygen

PaCO₂ will be kept in the range:

- 35 - 40 mm Hg for brain injury
- 35 - 50 mm Hg for normal lung, mild and moderate ARDS, COPD subjects without chronic hypercapnia
- ≥ 50 mm Hg in severe ARDS, severe COPD, and subjects with chronic hypercapnia if pH > 7.25

B. Passive subjects:

i. Ventilator settings:

Tidal volume will be kept in the range:

- 6-10 mL/Kg IBW for normal lung subjects, brain injury, and COPD subjects
- 4-8 mL/Kg IBW for ARDS

ii. Lung protection monitoring:

Plateau pressure will be measured at least twice a day and kept below 30 cmH₂O. Driving pressure will be measured at least four times a day and kept below 15 cmH₂O in all subjects.

In ARDS subjects, Plateau pressure between 30 and 35 cmH₂O will be accepted if driving pressure remains below 15 cmH₂O.

If plateau pressure exceeds 35 cmH₂O or driving pressure exceeds 15 cmH₂O, tidal volume will be decreased by 1 mL/Kg IBW keeping it above 4 mL/Kg or inspiratory pressure will be decreased by 2 cmH₂O.

iii. Additional and rescue procedures:

Continuous myorelaxant infusion, repeated recruitment maneuvers, nitric oxide, and prone position will be considered as additional procedures at the clinician's discretion.

If PaO₂ ≥ 55 mmHg or SpO₂ ≥ 88% with FIO₂ of 1.0 cannot be maintained, clinicians may employ rescue procedures. APRV, high frequency ventilation, ECCO2R and ECMO will be considered as a rescue therapies. The subjects will continue to be followed and included in the analysis on an intention-to-treat basis. Failure of the protocol and subsequent need for rescue therapy will constitute a secondary outcome. Control group subjects will not be allowed to cross-over to the INTELLiVENT-ASV group.

C. Spontaneous breathing subjects:

i. Ventilator settings:

Ventilation support will be adjusted to keep tidal volume in the range:

- 6-10 mL/Kg IBW for normal lung subjects, brain injury, and COPD subjects

- 4-8 mL/Kg IBW for ARDS

Ventilation support will be adjusted to keep respiratory rate \leq 35 Breaths/min.

Inspiratory trigger settings will be set between 1 and 5 L/min or 0.5 and 2 cmH₂O or activate Intellisync+.

Expiratory trigger setting will be set between 10 and 80% of the maximal inspiratory flow or activate Intellisync+.

Pressure rise time will be set between 0 and 400 ms.

Automated tube compensation if appropriate.

D. Weaning:

The INTELLiVENT-ASV or control arm ventilator protocols will be continued until subjects are able to breathe unassisted for 48 hours, death, ICU discharge, study withdrawal, if the site's principal investigator determines that the study is no longer in the subject's best interest or day 28, whichever comes first.

i. Screening of readiness to wean criteria

A screening of readiness to wean criteria will be performed twice a day between 6h00 and 18h00 for all subjects mechanically ventilated for more than 24h.

ii. Extubation

After a successful weaning trial, extubation criteria will be assessed:

- Coma Glasgow Score > 8
- Ability to cough
- Ability to swallow
- Absence of severe upper airway obstruction
- Successful cuff leak test

If all these criteria are fulfilled, subject will be extubated within 12 hours after the successful weaning trial.

iii. Ventilation management after extubation

High flow nasal treatment, CPAP, and NIV can be used after extubation.

iv. Definition of unsuccessful extubation

If reintubation occurs within 48-hours of extubation, this event will be noted as a reintubation.

v. Completion of ventilator procedures.

Subjects will be considered to have completed the study ventilator procedures if any of the following conditions occur:

1. Death
2. ICU discharge
3. Subject or proxy withdraws consent

4. Principal investigator of site determines that the trial is no longer in the subject's best interest
5. Completed a period of 48 hours of unassisted breathing.

If a subject requires positive pressure ventilation after a period of unassisted breathing, these will be at the discretion of the team caring for the subject.

E. Tracheostomy

The following recommendations to be consider for Tracheostomy.

Tracheostomy will only be performed on strict indications and preferably not earlier than 10 days after intubation.

Indications for tracheostomy will be:

- Failure to intubate
- Expected duration of mechanical ventilation > 14 days
- Glasgow Coma Score < 7 and/or inadequate swallow or cough reflex with sputum retention
- Severe ICU-acquired weakness
- Prolonged or unsuccessful weaning
- Repeated respiratory failure after extubation

Readiness to wean criteria will be the same as intubated subjects. The weaning schedule for unassisted ventilation with a tracheostomy will follow the local protocol of the participating centers.

F. Sedation

Sedation will be prescribed with a sedation target using RASS or RAMSAY scale re-assessed at least once a day. Sedation will be monitored at least 2 times a day.

A daily cessation of sedation will be performed if there is no contraindication.

The subject's study follow up ends after 28 days after enrollment, even if subject remains on mechanical ventilation. During this 28 days period, for subjects reintubated within 48h after extubation, VFD will not be counted and ventilator protocols will be continued. Subject re-intubated beyond 48h will be considered as weaned for ventilator and ventilator procedures will not be continued.

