10.5 Missing Data

Please refer to section 7.2 "Inclusion Criteria" and 8.4 "End of study".

Subject will be considered to have completed the study for the following reasons:

- Subject completes follow-ups (Day 28) required per investigational plan.
- Subject dies.
- Subject or legally authorized representative requests to be withdrawn from the study.
- Investigator requests to be withdrawn from the study to protect the welfare of the subject. (In that case, it is at the site's principal investigator's discretion to determine that the study is no longer in the subject's best interest).

The sponsor deems a dataset "complete" if both of the following conditions are achieved:

1. Minimum of 24h of recorded data available
2. Minimum of 80% of the total invasive ventilation within the allocated randomized ventilation mode time has been recorded.

An incomplete dataset leading to a dropout in the study is a dataset that misses at least one of the above mentioned variables.

The reason for an incomplete dataset can be:

- Early termination of recording caused by a transfer to another ICU
- Subject or legally authorized representative requests to be withdrawn from the study.
- Site's Principal Investigator's decides to stop the inclusion for any reason.
- Technical failure in recording.
- Less than 80% the invasive ventilation within the allocated randomized ventilation mode duration have been recorded in the Memory Box.
- Recorded data is less than 24h.

Dropout could occur when patients are ventilated for less than 24 hours after inclusion because of: unexpected death, transfer to another ICU, or withdrawal of informed consent. We expect a maximum of 5% of these cases.

Note a maximum of 5% of subjects are anticipated for which not 80% of mechanical ventilation time within the allocated randomized ventilation mode could be recorded due to documented technical reason. The recorded data will be used (with 'percent spent' calculated per the recorded time) for the primary analysis of the co-primary endpoints. As a sensitivity analysis, these values will be treated as missing data.

Because technical failure in recording may not be detected on time by the investigators, a continued enrollment is planned.

Technical issue in capturing the necessary data, the dropout probability is assumed to be equal for all subjects, regardless of their condition and ventilation modalities. Therefore, replacing subjects without collected data is not expected to cause any bias.

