11.2 Data management

11.2.1 Data Management Responsibilities

Study CRFs will be developed by the data manager and statistician in conjunction with Hamilton Medical. Quality control reports and queries will be routinely generated and distributed automatically by the eCRF to the study sites for verification and resolution. As part of the study activation process, the study site must identify all CRFs or part of the CRFs to be used as source documents.

Subject's ventilation data in both arms are directly recorded from the ventilators via a serial port using a Memory Box. The Memory Boxes are compatible with all Hamilton Medical ventilators.

This memory box contains a memory card and is solely for investigational use and is just basically saving output data from the ventilators. These data will not be cleaned due to the automated nature of the subject recordings.

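### Protocol 8.3.1 ends study data collection when the site investigator decides the study no longer serves the subject, so both co-primary endpoints can be missing for a reason tied to the allocated mode

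*Protocol*

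**What the plan says.** Protocol 8.3.1 (General management in both groups) covers the case where the site's principal investigator finds that the study, expressly including the randomised mode, no longer serves the subject. It then states that "the subject's ventilation and study data collection ends", and adds: "The site needs to complete an AE and the End of Study eCRF". Protocol 8.5 and 10.5 count an investigator withdrawal as completion of the study. Protocol 10.5 also lists among the causes of an incomplete dataset: "Site's Principal Investigator's decides to stop the inclusion for any reason".

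Other text points the other way:

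- Earlier in 8.3.1, "all ventilation variables will be continuously recorded from inclusion to extubation or death".
- For subjects who need rescue therapy (8.3.1 B.iii), "The subjects will continue to be followed and included in the analysis on an intention-to-treat basis".
- Protocol 10.4.2 and SAP 4.3.1 define the primary efficacy population as all randomised subjects, analysed as randomised.
- SAP 8.1 plans to describe the time spent in each mode for INTELLiVENT-ASV subjects who switched.

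On partial recordings, Protocol 10.5 says: "The recorded data will be used (with 'percent spent' calculated per the recorded time) for the primary analysis of the co-primary endpoints". This follows a sentence about recordings that fall short of 80% for documented technical reasons, and SAP 4.8 ties it to the same reasons.

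**The concern.** The outcome stops being observed because someone judged the allocated mode, or the study as a whole, unsuitable for that subject. That is informative missingness, and it comes from the protocol rather than from a refusal by the subject. It affects both co-primary endpoints, since both are percentages of recorded ventilation time up to Day 7.

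The rule applies to both arms. Stops caused by the mode itself may still fall more on one arm: Protocol 3.4 lets the physician return to conventional ventilation at any time, 8.3.1 bars control subjects from crossing over, and 9.1.3 (item 11) foresees a change of mode attributed to the mode. If so, the loss would bear on the treatment comparison in a pivotal trial, as well as on precision.

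Day 28 outcomes are also exposed. The Day 28 telephone call is specified for transferred subjects (Protocol 5.2, 7.6) and for re-intubation beyond 48 hours (8.4), but not for an investigator's stop.

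**Working it through.** **1. Which value enters the analysis?** Under ITT the stopped subject must contribute a value. The documents allow two readings.

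- The percentage over time recorded before the stop. This is specified only for technical shortfalls, so it does not clearly apply.
- An imputed value. SAP 4.8 imputes both arms under a missing-at-random model for the control arm. It also puts study arm first in the covariate list, which sits badly with a control-arm model. Own-arm and control-arm imputation are therefore both shown below.

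The MITT analysis requires 80% recording within the allocated mode (Protocol 10.4.3), so it may exclude the same subjects. The 5% dropout allowance (10.2) names death, transfer and consent withdrawal, not investigator stops. The argument in 10.5 that replacement causes no bias concerns technical failure only.

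**2. The plan's own figure.** Inputs (Protocol 10.2, logit scale): efficacy means -1.86 and -1.28, SD 1.5; safety means -0.09 and -0.74, SD 1.6; correlation -0.85; one-sided 0.025; power 0.80.

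Fixed design, per arm: n = 2 × (1.960 + 0.842)² × (SD / difference)².

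- Efficacy: 15.70 × (1.5 / 0.58)² = 105.
- Safety: 15.70 × (1.6 / 0.65)² = 95.1, rounded up to 96.

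Simulation with the Table 5 boundaries, binding futility and both endpoints required gives joint power 0.80 at 254 subjects. The planned sample size is reproduced, and this point does not change it.

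**3. Size of the bias.** The stop rate is not in the documents, so the share f of the INTELLiVENT-ASV arm is assumed to be 2-10%. Bias = f × (value entered - true value). The planned mean of -1.28 is taken as the mean of subjects not stopped.

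- Case A: the true value equals the control mean, -1.86. Own-arm imputation enters -1.28, an error of 0.58. Control-arm imputation enters -1.86, an error of 0.
- Case B: the true value is 1 SD below the arm mean, -1.28 - 1.5 = -2.78. Own-arm error is 1.5. Control-arm error is -1.86 - (-2.78) = 0.92.

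| f | A, own-arm | A, control-arm | B, own-arm | B, control-arm |
|---|---|---|---|---|
| 2% | 0.012 | 0 | 0.030 | 0.018 |
| 5% | 0.029 | 0 | 0.075 | 0.046 |
| 10% | 0.058 | 0 | 0.150 | 0.092 |

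As a share of 0.58, case B runs from 5% to 26% with own-arm values and from 3% to 16% with control-arm imputation.

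The same arithmetic for safety (difference 0.65, SD 1.6) gives 0.013-0.065 in case A. Case B gives 0.032-0.16 with own-arm values and 0.019-0.095 with control-arm imputation (error 1.6 - 0.65 = 0.95).

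**4. Effect on error rate.** If true differences were zero and both endpoints carried the full 1 SD bias, the simulated chance of rejecting on both is about 0.016, 0.029 and 0.067 at f = 2%, 5% and 10%. Without bias it is 0.011.

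**The case against.** A reader might infer that recording stops whenever a subject leaves the randomised mode. The documents do not say so. Switch-offs for procedures and switches made in error are allowed for in 8.3.1 without ending collection, and SAP 8.1 and Listing 16.02.07.01 expect data after a switch. The trigger is the investigator's best-interest decision about the study.

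A reader might also infer that the percentages rest on favourable time before the stop. That is not supported. If the mode was failing, the earlier time may be the poor time, and using it could count against the device.

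The SAP is not silent. Control-arm imputation in both arms is aimed at this kind of bias, and SAP 7.4 adds tipping-point and shift analyses for primary efficacy. These stand as partial mitigation. Control-arm imputation does not correct outcomes worse than control, and no missing-not-at-random analysis is named for the co-primary safety endpoint.

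Nor are Day 28 outcomes necessarily lost. Protocol 7.6 asks for every reasonable effort at a final evaluation, and the End of Study list in 8.4 includes mortality and length of stay. That makes Day 28 status possible but does not secure it.

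The rescue-therapy text is not a direct contradiction, because rescue happens within the study whereas an investigator's stop is treated as leaving it. The firmer conflict is with recording to extubation or death.

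Finally, the stop rate may be very low. Annex A cites two randomised studies with no safety issue requiring premature interruption of the mode. Figures such as 13-26% of the planned effect need 5-10% stopped, a true value 0.92 logit below the control mean and no control-arm imputation, so they cannot be the headline.

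**Conclusion.** The point holds in this limited form. An investigator's best-interest decision ends data collection, the missingness is informative, and the rule conflicts with the general recording rule and with the ITT population. It also sits badly with the follow-up kept for rescue therapy and with the planned description of time in both modes. The value entering the primary analysis after such a stop is undefined.

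The size rests wholly on assumptions. At 2-10% stopped in one arm, the efficacy bias ranges from about zero to 0.09 logit if control-arm imputation is applied as described, and up to 0.15 if it is not. The direction is not established, since it depends on which value is used and on how these subjects fared. This is a worthwhile and cheap correction, not a demonstration that the result would be biased in favour of the device.

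**What to change.** Reconcile Protocol 8.3.1 (all three statements), Protocol 10.5 and SAP 4.8 and 8.1 as follows:

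- A best-interest decision by the investigator does not by itself end data collection. Unless consent is withdrawn, Memory Box recording continues to Day 7 or extubation while the subject remains on a compatible Hamilton ventilator with SpO₂ and PetCO₂ sensors, and Day 28 status is collected.
- All recorded time is analysed in the randomised arm for the ITT analysis.
- The SAP states which value enters when recording is impossible, and resolves the control-arm model against study arm as a covariate.
- The shift and tipping-point analyses are extended to the co-primary safety endpoint.

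The cost is a short protocol and SAP amendment, some extra recording and a Day 28 contact for these subjects. Protocol 11.2.1 says "The Memory Boxes are compatible with all Hamilton Medical ventilators", so the recording equipment is not an obstacle while the subject stays on one. Decisions on ventilation mode and on when study ventilation ends stay with the clinicians and are not changed.
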